#### **4.1.3 Part A1 – Dose optimization (alternative dosing schedules)**

Part A1 is a multicenter, non-randomized, open-label, dose optimization module of Study ONC001 to evaluate alternative dosing schedules and infusion times for UCB6114 administered as monotherapy in patients with unresectable locally advanced or metastatic colorectal cancer, gastric cancer, cancer of the gastro-esophageal junction, or pancreatic cancer.

Part A1 may commence after the fifth cohort in Part A (Cohort 5) is considered sufficiently █ by the SMC (DLT rate less than 33%). The planned dose optimization scheme for Part A1 will assess the safety and tolerability of the drug new formulation and will explore shortening of the infusion time and less frequent dosing as follows:

- Cohort 1: 2000mg Q2W (60-minute iv infusion), 28-day treatment cycle
- Cohort 2: 2000mg Q2W (30-minute iv infusion), 28-day treatment cycle
- Cohort 3: 3000mg Q3W (90-minute iv infusion), 21-day treatment cycle
- Cohort 4: 4000mg Q4W (120-minute iv infusion), 28-day treatment cycle

Details of each planned cohort are provided in [Table 6-6](#).

Up to 32 participants will be allocated 1:1:1:1 to one of the 4 cohorts, with each cohort enrolling 8 study participants including 1 sentinel participant with an observation period of 48 hours.

The enrollment of a sentinel participant in each cohort has been included as an additional risk mitigation measure to monitor infusion related reactions and other early onset treatment-related AEs. Each sentinel participant will be assessed for at least 48 hours following the first administration of UCB6114 in the first cycle and the SMC will convene before further participants within the cohort can be enrolled.

The SMC will also convene after 25%, 50% and 100% of study participants in Part A1 have completed the required 28-day observation period. If deemed necessary, an additional SMC meeting can convene after 75% of the participants have completed the required observation period. If 1 DLT, or more, (refer to Section 4.1.2.4 for the definition of DLTs) are reported for a cohort then, an ad-hoc SMC will convene to determine if the dosing schedule and study can continue as planned.

If 3 or more participants experience DLT(s) in a given cohort, no further participants will be enrolled in the cohort and the dosing schedule will be considered to be unacceptably toxic.

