### **6.6.1.3 Within participant dose modification in Part A1**

Dose adjustments and/or changes in dosing schedule are not permitted.

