### 6.6.2.2 UCB6114 dose modifications

Study participants who experience Grade 4 (life-threatening) nonhematologic toxicity, including diarrhea and mucositis, which is at least possibly related to UCB6114, will be discontinued from treatment.

Treatment with UCB6114 may temporarily be suspended for up to 3 weeks beyond the scheduled treatment day until toxicities are resolved to CTCAE Grade 2 or less. If UCB6114 is

held for more than 3 weeks beyond the scheduled treatment day, then the participant will be discontinued from treatment and will be followed up for safety and efficacy per the Schedules of Activities for Part A ([Table 1-4](#)), Part B ([Table 1-7](#)), and Part C ([Table 1-8](#)).

For permitted adjustments of the infusion rate in case of AEs refer to the IMP Handling Manual. Participants who experience severe or life-threatening infusion-related events (CTCAE Grade 3 or 4) will not receive further infusions. Hypersensitivity/infusion-related events should be managed per institutional guidelines. Premedication with steroids may be administered at the discretion of the investigator.

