#### 6.6.3.2 UCB6114 dose modifications

Study participants who experience Grade 4 (life-threatening) nonhematologic toxicity, including diarrhea and mucositis, which is at least possibly related to UCB6114, will be discontinued from treatment.

Treatment with UCB6114 may temporarily be suspended for up to 3 weeks beyond the scheduled treatment day until toxicities are resolved to CTCAE Grade 2 or less. If UCB6114 is

held for more than 3 weeks beyond the scheduled treatment day, then the participant will be discontinued from treatment and will be followed up for safety and efficacy per the Schedule of Activities.

For permitted adjustments of the infusion rate in case of AEs, refer to the IMP Handling Manual. Participants who experience severe or life-threatening infusion-related events (Grade 3 or 4) will not receive further infusions. Hypersensitivity/infusion-related events should be managed per institutional guidelines. Premedication with steroids may be administered at the discretion of the investigator.

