### 7.1.3 Other criteria for discontinuation of study medication

Participants must discontinue study treatment if they experience any of the following:

1. There is confirmation of a pregnancy during the study, as evidenced by a positive pregnancy test.
2. The participant experiences unacceptable toxicity.
  - For information on dose delays due to drug-related toxicity, see Section [6.6.1](#) (Part A and Part A1), Section [6.6.2](#) (Part B), and Section [6.6.3](#) (Part C). Participants will discontinue treatment, unless, in the opinion of the investigator, they are experiencing clinical benefit and it is in their best interest to continue treatment. For these participants, treatment may continue at a reduced dose at the discretion of the investigator and Sponsor.
3. The participant has documented evidence of progressive disease.
  - Participants with progressive disease before the end of Cycle 1 may be discontinued from study medication at the discretion of the investigator. Participants with progressive disease beyond Cycle 1 will be discontinued from study medication. In cases where progression is not clear and, in the opinion of the investigator, the participant may be having clinical benefit, the participant may continue treatment, but must be reimaged within 2 cycles of treatment.
4. The participant, for any reason, requires treatment with another therapeutic agent or modality for his/her cancer (with the exception of palliative bone-directed radiotherapy). In this case, discontinuation from the study treatment must occur before introduction of the new agent or modality.

---

5. Participant takes prohibited concomitant medications as defined in this protocol.

Participants who discontinue the study medication and/or study early will have end-of-study (SFU) procedures performed as shown in the Schedules of Activities for Part A ([Table 1-4](#)), Part A1 ([Table 1-5](#) and [Table 1-6](#)), Part B ([Table 1-7](#)), and Part C ([Table 1-8](#)).

See the Schedules of Activities for Part A ([Table 1-4](#)), Part A1 ([Table 1-5 and Table 1-6](#)), Part B ([Table 1-7](#)), and Part C ([Table 1-8](#)) for data to be collected at the time of study treatment discontinuation and follow-up and for any further evaluations that need to be completed.

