### **9.2.9 Infusion-related reactions (hypersensitivity reactions)**

Participants should be observed for at least 6 hours after the start of the first infusion and for 2 hours after the start of the subsequent infusions for symptoms like fever and chills or other infusion-related symptom. Interruption or slowing the rate of the infusion may help control such symptoms. The infusion may be resumed when symptoms abate.

If an infusion-related reaction occurs, the participant must be treated according to the best available medical practice.

Participants should be instructed to report any delayed reactions to the investigator immediately.

Ensure that medications to treat infusion-related reactions, and cardiopulmonary resuscitative equipment are available for immediate use prior to initiation of UCB6114.

In the event of an infusion-related reaction, temporarily stop the drug until resolution, then resume at a reduced infusion rate.

If an infusion is interrupted, it can be restarted if the investigator considers it appropriate to do so. In such instances, the total infusion time may exceed the planned infusion time in order to administer the entire planned dose. The chronology of these events should be recorded accurately

in the source data and eCRF. In addition, the PK sampling times should be adjusted to preserve the relationship of sampling times to the start of the infusion.

If an infusion-related reaction or anaphylaxis occurs, a blood sample will be collected from the study participant as soon as possible, while the event is ongoing, to investigate the nature of the reaction. Evaluation of drug-related hypersensitivity reaction may consist of diagnostic testing and continued monitoring. Further tests may include, but are not limited to cytokine measurements, immunoglobulin E levels, tryptase, complement parameters such as C3a, C5a measurements when there is a suspicion of Type I or III hypersensitivity reaction.

The results of all monitoring, including laboratory testing and other testing, should be made available to the study site and Sponsor.

Premedication to prevent the onset of infusion-related reactions may be allowed for individual study participants based on the Investigator recommendations and after consultation with the Sponsor and should be recorded in the eCRF.

Procedures for reporting infusion-related reactions are the same as those for AEs and SAEs, as described in Appendix 3 (Section 11.3).

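### Section 9.2.9 sets no grade limit on resuming UCB6114 after an infusion reaction, at odds with the Grade 3-4 bar in Parts B and C; separately, the reduced-dose sentence in 7.1.3 is at odds with the Part A1 ban

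*Protocol*

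**What the plan says.** **Infusion reactions.** Section 9.2.9 is written for the whole study. Its one directive sentence is "In the event of an infusion-related reaction, temporarily stop the drug until resolution, then resume at a reduced infusion rate". Two further sentences are permissive: "The infusion may be resumed when symptoms abate", and, for an interrupted infusion, "it can be restarted if the investigator considers it appropriate to do so". The section names no CTCAE grade, separates no study parts and does not refer to Section 6.6.

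For Part B, Section 6.6.2.2 says: "Participants who experience severe or life-threatening infusion-related events (CTCAE Grade 3 or 4) will not receive further infusions". For Part C, Section 6.6.3.2 says the same: "Participants who experience severe or life-threatening infusion-related events (Grade 3 or 4) will not receive further infusions". Sections 6.6.1.2 (Part A) and 6.6.1.3 (Part A1) contain no equivalent rule.

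**Dose reduction.** Section 7.1.3 item 2 deals with unacceptable toxicity. Its bullet first refers the reader, for dose delays, to 6.6.1 (Parts A and A1), 6.6.2 (Part B) and 6.6.3 (Part C). It then requires discontinuation unless the investigator sees clinical benefit, and ends: "For these participants, treatment may continue at a reduced dose at the discretion of the investigator and Sponsor". For Part A1, Section 6.6.1.3 consists of one sentence: "Dose adjustments and/or changes in dosing schedule are not permitted".

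**The concern.** Rules for what happens after a severe reaction should give the same answer wherever a site looks. Staff managing a reaction will turn to 9.2.9, the section on that subject. Nothing there tells them that in Parts B and C a Grade 3 or 4 event ends UCB6114. At stake is re-exposure of a participant after a severe reaction, in a first-in-human study that uses sentinel participants in Parts A and A1 partly to watch for such reactions.

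The Part A1 point is smaller. That module exists "to evaluate alternative dosing schedules and infusion times for UCB6114 administered as monotherapy", with 8 participants per cohort. A participant who continues on a reduced dose is no longer on the cohort's defined dose, and one participant is 1/8 = 12.5% of a cohort. The same act would be allowed by one section and a breach of another.

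**Working it through.** This is a consistency check of stated rules. No power, alpha or event rate lies behind it, and the protocol gives no figure to reproduce.

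**Step 1. Does 9.2.9 reach severe reactions?** Yes. It gives fever and chills as example symptoms, but it also requires resuscitation equipment to be at hand, covers anaphylaxis, and provides for IgE, tryptase and complement testing. Its scope is not confined to mild events.

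**Step 2. Set the rules side by side for a Grade 3 infusion-related event in Part B or C.**
- 9.2.9, directive sentence: stop, then resume more slowly.
- 9.2.9, two permissive sentences: resumption is possible once symptoms abate, or if the investigator judges it appropriate.
- 6.6.2.2 and 6.6.3.2: no more infusions.

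The directive sentence conflicts with the bar. The permissive sentences do not compel a breach, but they offer a choice that the bar removes.

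**Step 3. Does any text say which governs?** No. 9.2.9 does not cite 6.6. Sections 6.6.2.2 and 6.6.3.2 send the reader to the IMP Handling Manual for rate adjustments, not to 9.2.9. The two places also differ on premedication: 9.2.9 asks for consultation with the Sponsor, while 6.6.2.2 and 6.6.3.2 leave steroid premedication to the investigator. This suggests that the sections were not aligned with each other.

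**Step 4. The Part A1 pair.** Table 6-2 lists UCB6114 as the only treatment in Part A1, at 2000, 3000 and 4000 mg by cohort, with no reduced level. A reduced dose there could only be a reduced dose of UCB6114, which 6.6.1.3 rules out. In Parts B and C the same sentence of 7.1.3 can be met by the chemotherapy reductions in 6.6.2.3 and 6.6.3.4, so it creates no dose-reduction conflict there.

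**Step 5. Reach.** All inputs are protocol figures.
- Parts B and C (Sections 4.1.4, 4.1.5): 27 + 27 = 54 participants at the enrolment caps.
- Planned UCB6114 infusions each: 2 cycles × 2 infusions (Days 1 and 15; Section 4.3.3.1) = 4.
- Planned infusions at the caps: 54 × 4 = 216. Participants who benefit may continue past 2 cycles, so this counts planned treatment only.
- Part A1 (Section 4.1.3): 4 cohorts × 8 = 32 participants.

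The protocol gives no rate for Grade 3-4 infusion reactions or for unacceptable toxicity, so these counts cannot be turned into expected cases.

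**The case against.** On infusion reactions, the defence is substantial. Two of the three resume sentences leave the site free not to restart, so declining after a Grade 3-4 event complies with both. The bars in 6.6.2.2 and 6.6.3.2 are specific, graded and absolute, and ordinary reading lets a specific prohibition limit a general management paragraph. The phrase on further infusions might also mean later doses rather than completion of the interrupted one. Other safeguards apply: management by institutional guidelines, mandatory discontinuation for related Grade 4 nonhematologic toxicity, DLT review by the SMC in Cycle 1, and the hold criteria in Section 6.7. The IMP Handling Manual is not at hand and may contain grade limits.

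Most of this stands and sets the size of the point. A reader might infer that the protocol orders sites to re-infuse after every reaction, including Grade 3-4. The documents do not support that, because 9.2.9 as a whole leaves room for judgement and the part-specific bar is the natural controlling text. What remains is that one sentence is unqualified, the section covers severe reactions, and nothing states the order of authority.

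On Part A1, the defence is that the part is named only in the cross-reference for dose delays, that the reduced-dose sentence names no part, and that the cross-reference leads to the section holding the ban. The sentence still has a use in Part A, where 6.6.1.2 permits adjustments after a DLT. A reader might infer that 7.1.3 expressly authorises reductions in Part A1; it does not. It is a general permission that fails to exclude the one part where reduction is forbidden. Section 9 disallows waivers, so Sponsor agreement cannot rescue a reduction. That supports 6.6.1.3 as the rule that should stand, but it does not remove the conflicting sentence.

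Nor does slowing an infusion under 9.2.9 breach 6.6.1.3: rate is neither dose nor schedule.

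**Conclusion.** Both inconsistencies are present in the current text and are worth correcting. They are conflicts between stated rules, not detail left to another document. Neither touches an endpoint definition, the sample size or the escalation rules.

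The first matters more, because it bears on re-exposure after a severe reaction. It reaches up to 54 participants and 216 planned infusions. The second reaches up to 32 participants. The number of actual cases under either is unknown and may be zero.

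The conclusion rests on the protocol text alone. If the IMP Handling Manual limits resumption by grade, the practical risk in Parts B and C is lower, but 9.2.9 would still need to agree with it.

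**What to change.** In Section 9.2.9, limit resuming or restarting to Grade 1-2 reactions and state that a Grade 3-4 reaction ends UCB6114 infusions. Cross-refer to 6.6.2.2 and 6.6.3.2 for Parts B and C, and say expressly that the same limit applies in Parts A and A1. Limiting the change to Parts B and C would imply that resuming after Grade 3-4 is acceptable in the other two parts, which have no bar now. The permission in 6.6.1.2 to adjust the dose after a DLT in Part A should be made subject to the new limit, so that no fresh conflict arises.

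In Section 7.1.3 item 2, add that the reduced-dose option does not apply to UCB6114 in Part A1.

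Avoid a general clause placing Section 6.6 above Section 7. The ban on schedule changes in 6.6.1.3 could then be read as removing the toxicity hold of up to 3 weeks that 7.1.4 allows in Part A1.

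The cost is a few sentences in the next amendment and a letter to sites, with no added procedures or participants. The one downside is that a few participants in Parts A and A1 would lose the option of rechallenge after a Grade 3-4 reaction.

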### **9.3 Safety signal detection**

Selected data from this study will be reviewed periodically to detect, as early as possible, any safety concern(s) related to the study medication so that investigators, study participants, regulatory authorities, and IRBs/IECs will be informed appropriately and as early as possible.

The study physician or medically qualified designee/equivalent will conduct an ongoing review of safety data as they become available and perform ongoing SAE reconciliations in collaboration with the Patient Safety representative.

As appropriate for the stage of development and accumulated experience with the study medication, medically qualified personnel at UCB may identify additional safety measures (eg, AEs, vital signs, laboratory or electrocardiogram [ECG] results) for which data will be periodically reviewed during the course of the study. For information regarding the SMC, see Section 4.1.1 (all parts), Section 4.1.2.1 (Part A), Section 4.1.3 (Part A1), Section 4.1.4.1 (Part B), and Section 4.1.5.1 (Part C).

### **9.4 Treatment of overdose**

For this study, any dose of UCB6114 >20% above the prescribed dose within a 24-hour time period will be considered an overdose. Overdose events are only considered AEs or SAEs if there are associated clinical signs and symptoms.

No specific information is available on the treatment of overdose for UCB6114.

UCB6114 will not be self-administered by the study participant. In the event of inadvertently administering an overdose of UCB6114, the investigator should:

[figure not shown]
1. Contact the study physician or medically qualified designee immediately.
2. Closely monitor the participant for any AE/SAE and laboratory abnormalities until UCB6114 can no longer be detected systemically (at least 28 days).

4. Document the quantity of the excess dose as well as the duration of the overdose in the eCRF.

[figure not shown]
Decisions regarding dose interruptions or modifications will be made by the investigator in consultation with the study physician or medically qualified designee based on the clinical evaluation of the participant.

For this study, overdose of the SOC combination therapies in Part B (TFD/TPI) and Part C (mFOLFOX6) refers to the administration of a quantity of medicinal product given per administration or per day that is above the recommended dose according to the authorized product information. This shall also take into account cumulative effects due to overdose. Please refer to the respective product information or SmPC for overdose management information.

## **9.5                   Pharmacokinetics**

**Table 9-4: Blood collection time points for PK analysis for Part A**

This table is completely redacted by a large black rectangular box.

**Table 9-4: Blood collection time points for PK analysis for Part A**

Time Point	Time Point Description
0	Baseline
1	1 hour
2	2 hours
3	3 hours
4	4 hours
5	5 hours
6	6 hours
7	7 hours
8	8 hours
9	9 hours
10	10 hours
11	11 hours
12	12 hours
13	13 hours
14	14 hours
15	15 hours
16	16 hours
17	17 hours
18	18 hours
19	19 hours
20	20 hours
21	21 hours
22	22 hours
23	23 hours
24	24 hours
25	25 hours
26	26 hours
27	27 hours
28	28 hours
29	29 hours
30	30 hours
31	31 hours
32	32 hours
33	33 hours
34	34 hours
35	35 hours
36	36 hours
37	37 hours
38	38 hours
39	39 hours
40	40 hours
41	41 hours
42	42 hours
43	43 hours
44	44 hours
45	45 hours
46	46 hours
47	47 hours
48	48 hours
49	49 hours
50	50 hours
51	51 hours
52	52 hours
53	53 hours
54	54 hours
55	55 hours
56	56 hours
57	57 hours
58	58 hours
59	59 hours
60	60 hours
61	61 hours
62	62 hours
63	63 hours
64	64 hours
65	65 hours
66	66 hours
67	67 hours
68	68 hours
69	69 hours
70	70 hours
71	71 hours
72	72 hours
73	73 hours
74	74 hours
75	75 hours
76	76 hours
77	77 hours
78	78 hours
79	79 hours
80	80 hours
81	81 hours
82	82 hours
83	83 hours
84	84 hours
85	85 hours
86	86 hours
87	87 hours
88	88 hours
89	89 hours
90	90 hours
91	91 hours
92	92 hours
93	93 hours
94	94 hours
95	95 hours
96	96 hours
97	97 hours
98	98 hours
99	99 hours
100	100 hours
101	101 hours
102	102 hours
103	103 hours
104	104 hours
105	105 hours
106	106 hours
107	107 hours
108	108 hours
109	109 hours
110	110 hours
111	111 hours
112	112 hours
113	113 hours
114	114 hours
115	115 hours
116	116 hours
117	117 hours
118	118 hours
119	119 hours
120	120 hours
121	121 hours
122	122 hours
123	123 hours
124	124 hours
125	125 hours
126	126 hours
127	127 hours
128	128 hours
129	129 hours
130	130 hours
131	131 hours
132	132 hours
133	133 hours
134	134 hours
135	135 hours
136	136 hours
137	137 hours
138	138 hours
139	139 hours
140	140 hours
141	141 hours
142	142 hours
143	143 hours
144	144 hours
145	145 hours
146	146 hours
147	147 hours
148	148 hours
149	149 hours
150	150 hours
151	151 hours
152	152 hours
153	153 hours
154	154 hours
155	155 hours
156	156 hours
157	157 hours
158	158 hours
159	159 hours
160	160 hours
161	161 hours
162	162 hours
163	163 hours
164	164 hours
165	165 hours
166	166 hours
167	167 hours
168	168 hours
169	169 hours
170	170 hours
171	171 hours
172	172 hours
173	173 hours
174	174 hours
175	175 hours
176	176 hours
177	177 hours
178	178 hours
179	179 hours
180	180 hours
181	181 hours
182	182 hours
183	183 hours
184	184 hours
185	185 hours
186	186 hours
187	187 hours
188	188 hours
189	189 hours
190	190 hours
191	191 hours
192	192 hours
193	193 hours
194	194 hours
195	195 hours
196	196 hours
197	197 hours
198	198 hours
199	199 hours
200	200 hours
201	201 hours
202	202 hours
203	203 hours
204	204 hours
205	205 hours
206	206 hours
207	207 hours
208	208 hours
209	209 hours
210	210 hours
211	211 hours
212	212 hours
213	213 hours
214	214 hours
215	215 hours
216	216 hours
217	217 hours
218	218 hours
219	219 hours
220	220 hours
221	221 hours
222	222 hours
223	223 hours
224	224 hours
225	225 hours
226	226 hours
227	227 hours
228	228 hours
229	229 hours
230	230 hours
231	231 hours
232	232 hours
233	233 hours
234	234 hours
235	235 hours
236	236 hours
237	237 hours
238	238 hours
239	239 hours
240	240 hours
241	241 hours
242	242 hours
243	243 hours
244	244 hours
245	245 hours
246	246 hours
247	247 hours
248	248 hours
249	249 hours
250	250 hours
251	251 hours
252	252 hours
253	253 hours
254	254 hours
255	255 hours
256	256 hours
257	257 hours
258	258 hours
259	259 hours
260	260 hours
261	261 hours
262	262 hours
263	263 hours
264	264 hours
265	265 hours
266	266 hours
267	267 hours
268	268 hours
269	269 hours
270	270 hours
271	271 hours
272	272 hours
273	273 hours
274	274 hours
275	275 hours
276	276 hours
277	277 hours
278	278 hours
279	279 hours
280	280 hours
281	281 hours
282	282 hours
283	283 hours
284	284 hours
285	285 hours
286	286 hours
287	287 hours
288	288 hours
289	289 hours
290	290 hours
291	291 hours
292	292 hours
293	293 hours
294	294 hours
295	295 hours
296	296 hours
297	297 hours
298	298 hours
299	299 hours
300	300 hours
301	301 hours
302	302 hours
303	303 hours
304	304 hours
305	305 hours
306	306 hours
307	307 hours
308	308 hours
309	309 hours
310	310 hours
311	311 hours
312	312 hours
313	313 hours
314	314 hours
315	315 hours
316	316 hours
317	317 hours
318	318 hours
319	319 hours
320	320 hours
321	321 hours
322	322 hours
323	323 hours
324	324 hours
325	325 hours
326	326 hours
327	327 hours
328	328 hours
329	329 hours
330	330 hours
331	331 hours
332	332 hours
333	333 hours
334	334 hours
335	335 hours
336	336 hours
337	337 hours
338	338 hours
339	339 hours
340	340 hours
341	341 hours
342	342 hours
343	343 hours
344	344 hours
345	345 hours
346	346 hours
347	347 hours
348	348 hours
349	349 hours
350	350 hours
351	351 hours
352	352 hours
353	353 hours
354	354 hours
355	355 hours
356	356 hours
357	357 hours
358	358 hours
359	359 hours
360	360 hours
361	361 hours
362	362 hours
363	363 hours
364	364 hours
365	365 hours
366	366 hours
367	367 hours
368	368 hours
369	369 hours
370	370 hours
371	371 hours
372	372 hours
373	373 hours
374	374 hours
375	375 hours
376	376 hours
377	377 hours
378	378 hours
379	379 hours
380	380 hours
381	381 hours
382	382 hours
383	383 hours
384	384 hours
385	385 hours
386	386 hours
387	387 hours
388	388 hours
389	389 hours
390	390 hours
391	391 hours
392	392 hours
393	393 hours
394	394 hours
395	395 hours
396	396 hours
397	397 hours
398	398 hours
399	399 hours
400	400 hours
401	401 hours
402	402 hours
403	403 hours
404	404 hours
405	405 hours
406	406 hours
407	407 hours
408	408 hours
409	409 hours
410	410 hours
411	411 hours
412	412 hours
413	413 hours
414	414 hours
415	415 hours
416	416 hours
417	417 hours
418	418 hours
419	419 hours
420	420 hours
421	421 hours
422	422 hours
423	423 hours
424	424 hours
425	425 hours
426	426 hours
427	427 hours
428	428 hours
429	429 hours
430	430 hours
431	431 hours
432	432 hours
433	433 hours
434	434 hours
435	435 hours
436	436 hours
437	437 hours
438	438 hours
439	439 hours
440	440 hours
441	441 hours
442	442 hours
443	443 hours
444	444 hours
445	445 hours
446	446 hours
447	447 hours
448	448 hours
449	449 hours
450	450 hours
451	451 hours
452	452 hours
453	453 hours
454	454 hours
455	455 hours
456	456 hours
457	457 hours
458	458 hours
459	459 hours
460	460 hours
461	461 hours
462	462 hours
463	463 hours
464	464 hours
465	465 hours
466	466 hours
467	467 hours
468	468 hours
469	469 hours
470	470 hours
471	471 hours
472	472 hours
473	473 hours
474	474 hours
475	475 hours
476	476 hours
477	477 hours
478	478 hours
479	479 hours
480	480 hours
481	481 hours
482	482 hours
483	483 hours
484	484 hours
485	485 hours
486	486 hours
487	487 hours
488	488 hours
489	489 hours
490	490 hours
491	491 hours
492	492 hours
493	493 hours
494	494 hours
495	495 hours
496	496 hours
497	497 hours
498	498 hours
499	499 hours
500	500 hours

